12.7.8.1 Procedure

After all the relevant data will be entered into the database, a soft lock to the database will be performed. The study statistician will perform the assessment of the primary and safety endpoints.

12.7.8.2 Decision Rules

Stop the study in case of severe safety concern.

13 STUDY PROCEDURES

13.1 General

1. The study will be conducted in compliance with this protocol, with GCP standards, and the applicable regulatory requirements.
2. This study will be cross-sectional, where patients will be enrolled, if possible, in a consecutive manner so as to prevent any bias. All patients with cirrhosis and without clinical signs of complications should be screened and reason for non-suitability documented.
3. Patients' relative or other representative will sign a consent/assent form prior to study participation.
4. A CRF will be filled out for each patient and all data will be collated incorporating all demographics, detailed clinical history, physiological variables, radiological data, biochemical data and organ support provided (cardiovascular, respiratory, renal, hepatic, neurological) and all baseline characteristics.
5. HVPG procedure will be performed in a standardized fashion in all study centers (see section 13.4 and Appendix II).
6. In addition, the tracings will be read at a centralized location by an independent expert reader. This independent analysis will be done by an expert reader blinded to the breath test results.
7. The *MBT* will be performed within 7 days (prior or post) of the HVPG procedure using a single dose of 75mg ¹³C-Methacetin. Note that the same

Exalenz Bioscience Ltd.	Last update on: Nov 21, 2016
Study Title: Clinical Study of the BreathID[®] MCS System to train the algorithm for the ¹³C-Methacetin Breath Test (MBT) in assessment of Portal Hypertension in Patients with Compensated Liver Cirrhosis	Protocol No.: CSPH-EX-0414 Version: 1.5
Document N^o: CSD00076	Page 42 of 72

policy should be applied with regards to the use of beta blockers as for the HVPG procedure for those patients that are treated with beta blockers. In case patient has a HCC, breath test has to be performed on the day of HVPG measurement.

8. If patient is using a stable dose of beta blockers, both the MBT and the HVPG procedures should be performed while continuing the stable dose even on the morning of each test.
9. All investigators will be blinded to the *MBT* score results until the end of the study recruitment. The *MBT* results will therefore not affect the current patient management.
10. Safety follow up will be done during the entire period of the study, and any adverse events will be recorded according to GCP ICH guidelines. Section 16.6 relates to the reportable and non-reportable SAEs.
11. Results of the individual blood tests and other clinical assessments, standard prognostic criteria and clinical condition of the patient will be collected in the CRF.
12. The raw data will be saved on the *BreathID[®] MCS* device and will be downloaded to a flash memory stick and uploaded to a computer for further analyses.
13. All concurrent medication will be recorded. Certain drugs will be pre-recorded in the CRF.
14. Patients' survival will be ascertained 30 days following their last breath test.
15. The breath test procedure is described in detail in the main protocol and it requires minimal operator and patient participation. *BreathID[®] MCS* automatic breath collection eliminates virtually all breath collection related errors, as described in section 13.3 and Appendix III.

Exalenz Bioscience Ltd.	Last update on: Nov 21, 2016
Study Title: Clinical Study of the BreathID[®] MCS System to train the algorithm for the ¹³C-Methacetin Breath Test (MBT) in assessment of Portal Hypertension in Patients with Compensated Liver Cirrhosis	Protocol No.: CSPH-EX-0414 Version: 1.5
Document N^o: CSD00076	Page 43 of 72

13.2 Masking procedures

In order to ensure unbiased interpretation of assay results, the following steps for masking will be taken:

- The authorized medical staff performing the HVPG procedure will be blinded to the breath test results.
- The principal investigator or co-investigator(s) will not be blinded to the results of HVPG and other diagnostic tests, since he may be the one performing the procedure and needs to evaluate the eligibility of the subject for treatment and/or possible monitoring as part of standard of care management.
- The blinding procedure is applicable only for the output of the *BreathID[®] MCS* device. The breath is collected and analyzed by the *BreathID[®] MCS* device and the results are printed out automatically at the end of the test. Hard copies of the device printouts will be stored with the CRFs as the source data.
- All HVPG tracing print outs will be stored as a hard copy or downloaded to a computer at the end of participation of each subject in the study, so that an independent analysis by a third party may be done.

13.3 Breath Test Procedure

Please refer to Appendix III and the IB for the MBT procedure

13.4 Principles of the Hepatic Venous Pressure Gradient (HVPG)

In order to standardize the measurements of the HVPG in the study the main procedure steps, derived from the common standards of care practice⁽¹⁰⁾, are described below in Appendix II.

Under conscious sedation and with non-invasive vital sign monitoring (ECG, arterial blood pressure and pulse oximetry) the right jugular vein (or the femoral or antecubital vein) is catheterized, a venous introducer is placed and a balloon-tipped catheter is advanced under fluoroscopic control into the inferior vena cava and a hepatic vein, to measure pressures. This is a moderately invasive technique that is only being performed as part of the clinical evaluation of the patient (and not solely for the purpose of the clinical trial) in common with other routine procedures that are carried out in patients with chronic liver injury.

Exalenz Bioscience Ltd.	Last update on: Nov 21, 2016
Study Title: Clinical Study of the BreathID[®] MCS System to train the algorithm for the ¹³C-Methacetin Breath Test (MBT) in assessment of Portal Hypertension in Patients with Compensated Liver Cirrhosis	Protocol No.: CSPH-EX-0414 Version: 1.5
Document N^o: CSD00076	Page 44 of 72

Free hepatic venous pressure is measured by maintaining the tip of the catheter “free” in hepatic vein, 2-4 cm from its opening into the vena cava. Wedge hepatic venous pressure is measured by occluding the hepatic vein by inflating a balloon at the tip of the catheter. The wedged hepatic venous pressure is measured until the value remains stable over 30-40 seconds. All measurements are performed in triplicate, permanent tracings are captured on a computer or chart recorder. The difference between the free and wedged hepatic venous pressures is the HVPG. Adequate occlusion of the hepatic vein is confirmed after pressure measurement, by slowly injecting 5cc of contrast into the vein that should show a typical “wedged” pattern without reflux of the contrast or its washout through communications with other hepatic veins.

Major complications have been limited to local injury at the puncture site, including leakage, hematoma and rarely an arteriovenous fistula or Horner syndrome. Ultrasonographic guidance reduces the risk of procedural complications. Passage of the catheter through the right atrium might cause supraventricular dysrhythmias that are self-limited in more than 90% of cases. Although coagulation disorders are common in patients with cirrhosis, only severe thrombocytopenia (platelets <20,000/mm³) calls for platelet transfusion. The procedure entails very little discomfort, is carried out under moderate conscious sedation that does not influence HVPG measurement. The procedure’s acceptability is comparable to that of upper gastrointestinal endoscopy.

Complications of the HVPG measurement will be reported as anticipated Adverse Events. The test procedure in this protocol is the MBT. The HVPG should be performed for clinical cause according to local standards of care; the HVPG will not be performed for the purpose of enrolling a patient under this protocol. For the purpose of the study, in US centers the HVPGs is considered an investigational procedure since HVPG is not used as common practice in the US.

13.4.1 Laboratory Tests

The patients will routinely undergo laboratory tests in preparation for their HVPG procedure. All liver related blood tests will be recorded along with other available laboratory information (as described below). If more than one blood collection is performed on a given day, the blood test results at the time closest to the time of the breath test will be recorded.

Recent (most recent, but within 6 months): blood test results will be recorded **if available**

Blood tests used as part of the pre-procedure safety evaluation for the HVPG procedure should be within 2 months (or sooner, if indicated by the patient’s co-morbid conditions).

1. aPTT, fibrinogen
2. Hepatic panel (AST, ALT, alkaline phosphatase, GGTP, total bilirubin, direct bilirubin, serum albumin and total protein)

Exalenz Bioscience Ltd.	Last update on: Nov 21, 2016
Study Title: Clinical Study of the BreathID[®] MCS System to train the algorithm for the ¹³C-Methacetin Breath Test (MBT) in assessment of Portal Hypertension in Patients with Compensated Liver Cirrhosis	Protocol No.: CSPH-EX-0414 Version: 1.5
Document N^o: CSD00076	Page 45 of 72

3. Renal and electrolyte panel (BUN, creatinine, electrolytes (Na⁺ and K⁺), total calcium, and PO₄ (phosphate corrected), magnesium
4. Blood count (WBC, Hemoglobin, Platelets)
5. Ammonia – arterial (preferred) or venous (if venous must be sampled from central vein not femoral or peripheral vein)

Additionally, assessments of the following variables will be made (not necessarily on days of breath test, but most recent within the past 6 months):

1. Ultrasound, CT (liver outline, vasculature, evidence of fat etc.), imaging of major hepatic vessels, pancreas, guts, and liver volume results if calculated; a single assessment of these variables when available.
2. Clinical data including: previous medical history, presentation, etiological factors, special diets and likely diagnosis on entry and update as available.
3. Habits and history of alcohol, substance and smoking will be recorded.
4. Liver Biopsy – if undertaken
5. Etiology, including etiological screening tests and diagnosis

13.5 Investigational Product Handling

The Investigator and Research Pharmacist (if relevant) will be provided with *Investigational Product Handling Guidelines* that will provide details regarding the packaging and labeling requirements, receipt of investigational product, dispensing and accountability procedures, preparation instructions, storage and stability of Investigational product, disposition of Investigational product, with the following forms required: Proof of receipt form, Temperature logs, Accountability logs, Investigational product and material transfer/ disposition form and pharmacy staff identification log (if applicable).

Local forms may be authorized for use after being approved by the Sponsor or his assigned representative.

13.6 Investigational Product Accountability

The Investigator and Study Pharmacist (if relevant) are responsible for ensuring that all study supplies received at the site are inventoried and accounted for throughout the study. The dispensing of study substrate to the subject must be documented in the respective accountability form. The study Investigational Product must be handled in strict accordance with the protocol and the container label and will be stored in a limited access area or in a locked cabinet under

Exalenz Bioscience Ltd.	Last update on: Nov 21, 2016
Study Title: Clinical Study of the BreathID[®] MCS System to train the algorithm for the ¹³C-Methacetin Breath Test (MBT) in assessment of Portal Hypertension in Patients with Compensated Liver Cirrhosis	Protocol No.: CSPH-EX-0414 Version: 1.5
Document N^o: CSD00076	Page 46 of 72

appropriate environmental conditions. Unused study materials must be available for verification by the sponsor's site monitor during on-site monitoring. The destruction of unused study materials (both, expired or unexpired) will be documented on the return/disposition form. The Sponsor will authorize to destroy excess supplies on site according to local policy. In this case, before proceeding, the site must seek authorization from the Sponsor using the return/destruction form and this must also be documented on the Study Supply Return Form.

Study substrate should be dispensed under the supervision of the investigator, a qualified member of the investigational staff, or by hospital clinical pharmacist.

14 ETHICS & REGULATORY CONSIDERATIONS

14.1 Ethics & Regulatory Approvals

The study will be conducted in both the United States of America and Europe (Spain and France). As such, regulatory requirements that are relevant for all countries will be discussed in this section.

The study will be conducted in compliance with the principles of the Declaration of Helsinki (1996), the principles of GCP and in accordance with all applicable regulatory requirements.

This protocol and related documents will be submitted for review to all relevant ethics committees delegated to approve the study at their respective sites. Any amendment to the protocol may be proposed by the principal investigator. The amendment must be submitted to the Sponsor and, when approved to the relevant IRB or EC. When applicable, the implementation of the amendment will take place only once approved by the appropriate ethics committee.

Annual progress and safety reports and a final report at conclusion of the study will be submitted by Exalenz Bioscience (or on behalf of the Sponsor) to the applicable regulatory bodies within the timelines defined in the Regulations.

15 INVESTIGATOR RESPONSIBILITIES

The investigator is responsible for ensuring that the clinical study is performed in accordance with the protocol, current ICH guidelines on GCP, and applicable regulatory requirements. GCP is an international ethical and scientific quality standard for designing, conducting, recording, and reporting studies that involve the participation of human subjects. Compliance with this standard provides public assurance that the rights, safety, and well-being of study subjects are

Exalenz Bioscience Ltd.	Last update on: Nov 21, 2016
Study Title: Clinical Study of the BreathID[®] MCS System to train the algorithm for the ¹³C-Methacetin Breath Test (MBT) in assessment of Portal Hypertension in Patients with Compensated Liver Cirrhosis	Protocol No.: CSPH-EX-0414 Version: 1.5
Document N^o: CSD00076	Page 47 of 72

protected, consistent with the principles that originated in the Declaration of Helsinki, and that the clinical study data are credible.

The investigational devices will bear an identification number and their accountability will be filed in the Investigator's Study File. Study supplies logged in will be kept by the investigator or the delegated persons in a secure place. All supplies (device, substrate and cannulae) will be used for this study only. After completion of the study, the device, drug and all unused accessories must be returned to Exalenz Bioscience Ltd. as per their request or alternatively, destroyed according to local regulations after receiving explicit authorization by Exalenz to do so and provide Exalenz with a confirmation.

The Principal Investigator will act as custodian for the study data. Patient data will be anonymized and all the anonymized data will be stored on a password protected computer. All data will be compliant with CFR and GCP.

16 SAFETY CONSIDERATIONS

16.1 *Adverse Event Definitions*

An adverse event (AE) is any undesirable or unintentional event that occurs in a patient or clinical investigation subject, whether or not considered related to the investigational product; this includes clinically significant changes in laboratory values. As this study is not therapeutic in nature, there will be no therapeutic failures to report.

Regardless of severity or relationship to the study investigational product, all diagnoses, symptom(s), sign(s) or finding(s) with a start date after the first study test has begun (Breath test/EGD) and until the last study procedure is being completed will be documented, assessed by the investigator and recorded in the subject's CRF.

A surgical procedure that was planned prior to the first study test by any physician treating the subject should not be recorded as an AE.

16.2 *Serious Adverse Event (SAE), Unanticipated Adverse Device Effect (UADE) and Suspected Unexpected Serious Adverse Reactions (SUSAR)*

A serious adverse event (SAE) is an event that is either:

- a) Fatal
- b) Life-threatening

Exalenz Bioscience Ltd.	Last update on: Nov 21, 2016
Study Title: Clinical Study of the BreathID[®] MCS System to train the algorithm for the ¹³C-Methacetin Breath Test (MBT) in assessment of Portal Hypertension in Patients with Compensated Liver Cirrhosis	Protocol No.: CSPH-EX-0414 Version: 1.5
Document N^o: CSD00076	Page 48 of 72

Life threatening is defined as an event in which the patient is at risk of death at the time of the event. It does not refer to an event that hypothetically might have caused death if it was more severe.

c) Results in persistent or significant disability/incapacity

Disability is defined as a substantial disruption of a person's ability to conduct normal life functions.

d) Requires or prolongs inpatient hospitalization

e) A congenital anomaly or birth defect.

f) Another serious or important medical event as judged by the investigator.

An Unanticipated Adverse Device Effect (UADE) or a Suspected Unexpected Serious Adverse Reactions (SUSAR) is an SAE, related to the investigational product, for which the nature or severity is not consistent with the expected outcomes of the treatment/testing being offered.

An unexpected adverse event is one that has not been previously observed, or one that is of a specificity or severity not consistent with the current investigator brochure.

As with every procedure risks and discomforts may occur with relations to the Breath ID test. The potential risks/complications and discomforts which may be associated with all study procedures are listed below.

- Allergic and/or other reactions to BreathID reagent
- Aspiration (inhaling) of food or fluids into the lungs
- Discomfort

When an adverse event occurs, the following information and assessments should be documented in the subject's file and reported in the adverse event section of the CRF:

- The signs, symptoms, or diagnosis of the event if available
- The date and time of onset of the event using the 24 hour clock where midnight is 00:00 and noon is 12:00
- The adverse event severity using the criteria outlined below
- The relationship of the event to the study medical device or drug as outlined below
- Describe any action taken regarding study medical device or drug disposition
- List any required therapy, medication, treatment, or diagnostic procedure.

Exalenz Bioscience Ltd.	Last update on: Nov 21, 2016
Study Title: Clinical Study of the BreathID[®] MCS System to train the algorithm for the ¹³C-Methacetin Breath Test (MBT) in assessment of Portal Hypertension in Patients with Compensated Liver Cirrhosis	Protocol No.: CSPH-EX-0414 Version: 1.5
Document N^o: CSD00076	Page 49 of 72

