Secondary:	
 1. Binary diagnosis of portal hypertension with HVPG ≥ 12 mmHg 2. Binary diagnosis of portal hypertension with HVPG ≥ 20 mmHg 3. Correlation of MBT with HVPG readings 4. Assess the effect of beta blockers or other confounding factors on the Correlation of MBT with HVPG readings 5. Examine the effect of a single small (<3cm) HCC (hepatocellular carcinoma) on the correlation of MBT with HVPG tracings
Safety Endpoints:	Safety will be assessed by all adverse and serious adverse events occurring in all subjects enrolled throughout the duration of the study.
Study Design:	A multicenter, non-randomized, blinded, cross-sectional comparative exploratory study comparing various MBT measures to HVPG. This study will be used to train an algorithm using MBT measures and to select a cut-off to determine presence or absence of CSPH as defined by HVPG ≥ 10 mmHg.

Exalenz Bioscience Ltd.	Last update on: Nov 21, 2016
Study Title: Clinical Study of the BreathID[®] MCS System to train the algorithm for the ¹³C-Methacetin Breath Test (MBT) in assessment of Portal Hypertension in Patients with Compensated Liver Cirrhosis	Protocol No.: CSPH-EX-0414 Version: 1.5
Document N^o: CSD00076	Page 12 of 72

Study Population^a:

At least 200 consecutive compensated cirrhotic patients, defined as cirrhotic patients without complications^b and meeting all inclusion/exclusion criteria will be enrolled on a walk-in basis. If beta blockers or HCC or other confounding factors affect the correlation between MBT and HVPG the sample size may be enlarged following interim analysis.

Inclusion Criteria:

1. Adult men or women (≥ 18 years of age)
2. Patient (or legal guardian) can sign an Informed Consent Form
3. Known chronic liver disease with cirrhosis confirmed by either:
 - a. liver biopsy or
 - b. clinical (palpable left lobe, splenomegaly) and laboratory (platelets $< 150,000/\text{mm}^3$ or albumin $< 3.8\text{g/dL}$, or INR > 1.3) evidence of cirrhosis and/or
 - c. imaging studies by abdominal sonography, computer assisted axial tomography, or magnetic resonance imaging, showing a nodular liver and/or enlarged spleen and/or portosystemic collaterals with portal vein patency and/or minimal ascites, and/or colloid shift on a colloid-isotope liver-spleen scan or measurements of liver stiffness suggestive of cirrhosis
4. Europe: Indicated to undergo HVPG testing
US: Consented for HVPG
5. Can tolerate an overnight (8-hour) fast

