5.4 Unmet need for a noninvasive tool for assessment of CSPH

Although HVPG is highly clinically valuable,⁽²⁶⁾ and the method used to measure HVPG is accurate, reproducible and reasonably safe,⁽¹⁵⁾ limitations to the generalized use of HVPG are a lack of local expertise and poor adherence to guidelines to ensure reliable and reproducible measurements.^(10, 13) Moreover, HVPG is an invasive intravascular procedure involving imaging, contrast media injection and catheterization. Hence HVPG is limited to large medical facilities requiring resources beyond the hepatology clinic and point of care physician and holds significant added risk to the patients. Berzigotti et al. in their recent review⁽³¹⁾ determined that HVPG is the best method to assess CSPH, but they also cite the limitations of the procedure, especially in the context of therapy monitoring:

“HVPG measurements are not available in all centers, the technique is invasive and some patients are unwilling to be submitted to it. This is even more relevant when the repetition of the procedure is needed to monitor treatment response. These issues have raised interest to non-invasively determine when CSPH is present, so allowing defining a patient at risk of developing portal hypertension-related complications.”⁽³¹⁾

Hence, HVPG is an impractical test for everyday clinical use. Serial HVPG measurements are likely to be useful but not practicable in clinical practice. Furthermore, key opinion leaders (KOL) have commented that many more HVPG measurements would be done if it was not for the practical drawbacks and limitations since it is felt to be a good predictor of complications of cirrhosis.^(12, 22) It is clearly desirable and necessary to have an equally reliable surrogate test that is non-invasive.

Moreover, although HVPG is clinically highly valuable,⁽²⁶⁾ even in experienced hands, complications can occur including large hematomas of the neck or groin being the most common (as reported in a leading Spanish center that regularly measures HVPG with a complication rate of 2.3%).

Exalenz Bioscience Ltd.	Last update on: Nov 21, 2016
Study Title: Clinical Study of the BreathID[®] MCS System to train the algorithm for the ¹³C-Methacetin Breath Test (MBT) in assessment of Portal Hypertension in Patients with Compensated Liver Cirrhosis	Protocol No.: CSPH-EX-0414 Version: 1.5
Document N^o: CSD00076	Page 23 of 72

5.5 ¹³C-Breath Tests

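### Section 16.1 sets an adverse event window that names a procedure this study does not have, omits HVPG and stops at the last procedure, in conflict with the synopsis, 13.1, 13.4 and 16.5

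*Combined protocol and SAP*

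**What the plan says.** Section 16.1 is the only place that gives adverse event recording both a start and a stop. Events are documented in the CRF if they occur "with a start date after the first study test has begun (Breath test/EGD) and until the last study procedure is being completed".

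Other sections are wider:

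- Synopsis, Safety Endpoints: "Safety will be assessed by all adverse and serious adverse events occurring in all subjects enrolled throughout the duration of the study".
- Section 13.1 item 10: "Safety follow up will be done during the entire period of the study, and any adverse events will be recorded".
- Section 13.4: "Complications of the HVPG measurement will be reported as anticipated Adverse Events".
- Section 16.5 asks the investigator to enter all adverse events in the CRF and to report any serious event to the sponsor within 24 hours. Neither duty carries an onset window.
- Section 16.6 exempts bleeding after line insertion from expedited notification but still sends it to the CRF follow-up section.

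The visit schedule (Section 4) lists adverse event reporting under Day 1-7, beside HVPG and MBT. The only later observation is in 13.1 item 14: "Patients' survival will be ascertained 30 days following their last breath test".

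**The concern.** The two tests in the synopsis list of procedures and in the visit schedule are HVPG and MBT. EGD appears in neither, nor in the abbreviations. The parenthesis in 16.1 therefore names a test that nobody will have and leaves out the invasive one. A site that follows 16.1 to the letter may start recording at the MBT even when HVPG came first, and may stop when the last procedure ends.

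Adverse event reporting is the study's only safety endpoint (10.5, 12.4). Under the literal window, how long a patient is observed, and which test's after-effects are seen, depends on test order, so the incidence tables in 12.7.4 would pool unequal periods. The stopping rule in 11.5 also counts Grade 3 and higher events and relies on the same capture. In US centres 13.4 treats HVPG as investigational, so part of the harm at issue there would come from a research procedure.

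**Working it through.** The plan gives no figure to reproduce. The check is a comparison of passages, plus simple arithmetic for scale.

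**Timing inputs**

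- MBT within 7 days before or after HVPG (13.1 item 7).
- HVPG under conscious sedation (13.4); no sedation in the 24 hours before the MBT (11.3 item 5). HVPG first therefore implies a gap of at least 24 hours if sedation is used.
- MBT session: 15-20 minutes of baseline, then up to 75 minutes after the dose (Appendix III), so at most 20 + 75 = 95 minutes.
- Allergic or other reactions to the reagent are a listed risk (16.2).

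**What the literal 16.1 window covers, by order**

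| Order | Inside | Outside |
|---|---|---|
| HVPG first, MBT last | Events starting during the MBT | Events starting from HVPG up to the start of the MBT (24 hours to 7 days if sedated); substrate reactions starting after the MBT ends |
| MBT first, HVPG last | Substrate reactions starting before HVPG ends (up to 7 days); events during HVPG | HVPG events starting after the procedure ends |

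**Scale for HVPG complications**

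Section 5.4 cites one Spanish centre "with a complication rate of 2.3" per cent. Applying that rate here is an assumption.

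- Expected complications = N × 0.023: 200 × 0.023 = 4.6, and 400 × 0.023 = 9.2 if the sample is enlarged.
- Probability of at least one in 200 = 1 − 0.977^200 = 99.0%.
- The share s of patients with HVPG first is not given. Expected complications in those patients = 4.6 × s for N = 200:

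| s | 0 | 0.25 | 0.50 | 0.75 | 1 |
|---|---|---|---|---|---|
| Expected | 0 | 1.15 | 2.3 | 3.45 | 4.6 |

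These are upper bounds on what is lost before the window opens, because a complication that starts after the MBT has begun may still fall inside it. The total of 4.6 is also the ceiling for losses at both ends of the window together.

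**Scale for related events**

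If no related event is seen in 200 patients, the exact two-sided 95% upper limit is 1 − 0.025^(1/200) = 1.83%. For patients whose MBT is last, and under the literal window, that limit would describe little more than the test session.

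**Which analyses are touched**

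The rate with an exact interval in 12.7.4 covers events related to drug or device, and 16.3 defines related as associated with the device or substrate. A catheter haematoma would not enter that rate under any window; it belongs in the all-event tables. A delayed substrate reaction could affect both.

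**The case against.** A reader might infer that HVPG complications fall outside the safety data altogether. The documents do not support that. Section 13.4 commits to reporting them, 16.5 asks for all adverse events and for any serious event within 24 hours without an onset limit, 16.6 routes line-insertion bleeding to the CRF, and the visit schedule places adverse event reporting beside both tests. A serious late event has a reporting route whatever 16.1 says.

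The literal reading of 16.1 is also not the only one. The governing phrase is the first study test, and the parenthesis can be read as a faulty gloss on it. Patients with HCC must have the MBT on the day of HVPG; if HVPG is sedated, the 24-hour rule puts their MBT first, so the window opens before HVPG. Because 16.1 works by start date, an event later on the MBT day is not clearly excluded.

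These points stand, and they limit the finding to an inconsistency. They do not remove it. None of the wider passages says when an individual patient's collection ends, and the period of the study is not defined per patient. Some text favours the narrow reading: 13.4 states that "The test procedure in this protocol is the MBT", and the 16.2 list of risks, said to cover all study procedures, contains no vascular-access complication. A site can comply with 16.1 and breach 13.1 and 13.4.

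**Conclusion.** Section 16.1 is wrong as written and contradicts the synopsis, 13.1 item 10, 13.4 and 16.5. Its opening event names EGD and omits HVPG, and its close leaves no stated collection after the last procedure. The gap is clearest for a substrate reaction that starts after a final MBT, since no other passage sets an end date that would plainly include it.

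For HVPG complications, the possible loss before the window opens is between 0 and 4.6 expected events in 200 patients (0 to 9.2 in 400). This assumes that the one-centre 2.3% rate applies, that 16.1 is read literally, and that 13.4 and 16.5 are disregarded. The figure of 4.6 should not be read as a forecast of missed events. The effect is on the all-event tables and, for delayed substrate reactions, on the related-event rate in 12.7.4. The primary AUC analysis is untouched. The change should be made, but it is of moderate weight.

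**What to change.** In 16.1, replace (Breath test/EGD) with: HVPG or MBT, whichever comes first. Then state one end of adverse event collection that falls after the last procedure and is the same for every patient, and use it in 12.7.4, 13.1, 16.1 and the visit schedule.

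The 30-day survival ascertainment in 13.1 item 14 is one possible anchor. As written it covers survival only and the visit schedule lists no such contact, so using it means adding an adverse event question and a scheduled contact. It would also collect some expected disease events, which 16.6 already anticipates. The documents do not show that 30 days is the necessary length, so the sponsor may justify a different end, provided it is stated once and applied to all.

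The cost is a short protocol amendment and, if the 30-day anchor is chosen, one brief contact per patient.
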